### **3.2 Rationale for study design, doses and control groups**

The primary objective is to determine the IPA profiles of single and multiple doses of ticagrelor 45, 60, and 90 mg in Chinese patients with stable coronary heart disease on chronic low dose ASA. The primary variable is IPA, final extent (20 $\mu$ M ADP). Previous exposure of ticagrelor in China includes healthy patients (D5130C00054) and ACS patients (D5130C05262), but not stable coronary heart disease. This study will explore three doses of ticagrelor in order to determine the IPA, PRU and pharmacokinetic profile in Chinese patients with stable coronary heart disease. The VerifyNow System is a commercially available system to measure inhibition of P2Y12 receptor and is considered appropriate for this study. Holter monitoring and an echocardiogram will be obtained prior to dosing in order to rule out those at risk for bradyarrhythmias and potential indications for anticoagulation. See Section 4.2

This is an open label, single centre, randomised, Phase IV, pharmacodynamic, pharmacokinetic, and safety study. There is no control group.

Treatment for 4 days with bid dosing of the study allows ticagrelor to reach steady-state, and hence allows Day 7 results to be compared with the Day 1 dose of each drug dose level.

#### **Ticagrelor dosing regimen**

The approved loading dose of ticagrelor is 180 mg followed by 90 mg bid in patients with ACS. There is no approved dose for chronic coronary heart disease. Therefore, this study will examine 45, 60 and 90 mg doses of ticagrelor in order to determine the IPA and PK profile in Chinese patients with stable coronary heart disease.

#### **Background Therapy**

Ticagrelor will be administered against a background of ASA therapy, since ASA is standard therapy for the prevention of thrombotic events and new therapies will be adjunctive in this patient population (Matetzky S et al 2004, Hongo RH et al 2002, Aleil B et al 2005, Barragan P et al 2003). A once daily ASA dose of 75 mg to 100 mg is being used as that is the dose that has been approved for chronic therapy with ticagrelor. The ASA dose of 75 to 100 mg has been recommended since previous clinical studies (Chen ZM 2005, Peters RJG et al 2003, Price MJ et al 2006, Sabatine MS et al 2005) have indicated this as a suitable daily dose range for ASA in combination therapy to protect against thrombotic events. Each patient's ASA dose should remain constant throughout the study. As ticagrelor has not been approved with doses of ASA above 100mg, doses greater than 100mg will not be studied. Patient requiring greater than 100mg ASA will not be enrolled in the study.

## **4. PATIENT SELECTION CRITERIA**

Investigator(s) should keep a record, the patient screening log, of patients who entered pre-study screening.

Each patient should meet all of the inclusion criteria and none of the exclusion criteria for this study. Under no circumstances can there be exceptions to this rule.

#### **4.1 Inclusion criteria**

For inclusion in the study patients should fulfil the following criteria:

1. Provision of signed and dated written informed consent prior to any study specific procedures.
2. Female or male Chinese (as defined by Chinese Regulatory) patients aged 18 years or older with suitable veins for cannulations or repeated venipunctures.
3. Documented stable coronary heart disease (CHD) fulfilling all of the following, and taking 75-100 mg ASA daily treatment:

Diagnosed stable angina pectoris per the guidance of Chinese Society of Cardiology published in 2007, patients with angina severity classified as I and II of Canadian Cardiovascular Society grading of angina pectoris.

4. Female patients must meet one of the following conditions:
  - Post-menopausal defined as amenorrhoea for at least 12 months following cessation of all exogenous hormonal treatments and with follicle-stimulating hormone (FSH) levels in the laboratory defined post-menopausal range.
  - Documentation of irreversible surgical sterilisation by hysterectomy, bilateral oophorectomy or bilateral salpingectomy but not tubal ligation.
  - Women of childbearing potential must have a negative urine pregnancy test

#### **4.2 Exclusion criteria**

Subjects should not enter the study if any of the following exclusion criteria are fulfilled:

1. Any indication for oral anticoagulant (eg, atrial fibrillation, mitral stenosis or prosthetic heart valve) or dual antiplatelet treatment (eg, clopidogrel, prasugrel, or ASA). Also, chronic ASA with doses greater than 100 mg/day.
2. Concomitant therapy with strong CYP3A inhibitors, CYP3A substrates with narrow therapeutic index, or strong CYP3A inducers within 14 days preceding the first dose of study medication and during study treatment:
  - Strong inhibitors: ketoconazole, itraconazole, voriconazole, telithromycin, clarithromycin, nefazadone, ritonavir, saquinavir, nelfinavir, indinavir, atazanavir.

- Substrates with narrow therapeutic index: cyclosporine, quinidine
  - Strong inducers: rifampin/rifampicin, phenytoin, carbamazepine
  - Doses of lovastatin or simvastatin >40mg/day.
3. Increased bleeding risk including:
- Recent (within 30 days preceding the first dose of study medication) GI bleeding
  - Any history of intracranial, intraocular, retroperitoneal, or spinal bleeding
  - Recent (within 30 days of first dosing) major trauma
  - Sustained uncontrolled hypertension (systolic blood pressure [SBP] >180 mmHg or diastolic blood pressure [DBP] >100 mmHg)
  - History of hemorrhagic disorders that can increase the risk of bleeding, eg, haemophilia, von Willebrand's disease
  - Inability to discontinue required concomitant therapy with non-steroidal anti-inflammatory drug (NSAID) at screening. (Washout of NSAID, if currently taking, for at least 7 days or 5 half lives of the medication, whichever is longer)
  - Patients that have used within 30 days of screening, any oral or parenteral anticoagulant, including low molecular weight heparin.
  - Platelet count less than 100,000 mm^3 or hemoglobin <10 g/dL
4. Contraindication or other reason that ASA or ticagrelor should not be administered (eg, hypersensitivity, active bleeding, major surgery within 30 days of dosing, any bleeding tendency [coagulation defects], acute or chronic liver disease etc)
5. History of drug addiction or alcohol abuse in the previous 1 year
6. Positive screen for urine drugs of abuse
7. Positive screen for alcohol abuse (by alcohol breath test)
8. Current smokers, however, if <5 cigarettes per week, then not defined as smoker, and allow in study
9. Patient requires dialysis

10. Participation in another investigational drug or device study within 30 days prior to first dosing
11. Blood donation within 30 days of first dosing or any blood/plasma loss >500 mL during the 3 months prior to enrolment
12. Patients that are scheduled for revascularization (eg, PCI, CABG) during the study period
13. Any acute or chronic unstable condition in the past 30 days or other condition which, in the opinion of the investigator, may either put the patient at risk or influence the result of the study (eg, active cancer, risk for non-compliance, risk for being lost to follow-up)
14. History of moderate or severe hepatic impairment
15. Patients who in the opinion of the investigator would be at risk for bradycardia or have a HR $\leq$ 50.
16. Involvement in the planning and conduct of the study (applies to AstraZeneca or delegate staff, and study site staff)
17. Previous enrolment or randomisation of treatment in the present study
18. Patients who had ACS or stent placed within 12 months of screening
19. A suspected/manifest infection according to the World Health Organization (WHO) risk categories 2, 3, and 4
20. Currently taking ticlopidine or cilostazol
21. History of intolerance or allergy to ASA, clopidogrel, prasugrel, ticagrelor
22. Clinically significant deviation in physical findings or laboratory values as judged by the investigator.
23. Positive Serology (Hepatitis B surface antigen, Hepatitis C IgG, HIV Ab)
24. Concern for the inability of the patient to comply with study procedures and/or follow-up.

Procedures for withdrawal of incorrectly enrolled patients see Section 5.3.

## **5. STUDY CONDUCT**

### **5.1 Restrictions during the study**

1. Fast (except for water) for at least 8 hours before dosing for the morning dose on Day 1 and Day 7, and remain fasting until 2 h post-dose. Water is allowed until 1 h before, and from 1 h after dosing. Water (240 mL) needed for drug administration is allowed.
2. Eat and drink only the standardised meals and drinks provided (apart from water) during the residential period in the unit.
3. Abstain from consuming any of the following:
  - Alcohol from 72 h prior to enrolment visit, during the residential period and until the follow-up visit
  - Grapefruit, grapefruit juice, Seville oranges, Seville orange marmalade or other products containing grapefruit or Seville oranges and grapefruit from 7 days prior to initiation of investigational product (IP) until end of the treatment period
  - Refrain from taking any new medication (including traditional Chinese medication) during the 2 weeks prior to the first administration of IP until the follow-up visit, unless the investigator has given prior consent.
  - Abstain from blood or plasma donation until 3 months after the last dose of IP
  - Refrain from drugs of abuse from time of consent until after the final medical examination at the study follow-up
4. Stay at the study unit from Day -2 until 12 to 24 hours after Day 7 dosing of Visit 2. The stay might also be prolonged for safety reasons, if judged necessary by the investigator.
5. Patients of child bearing potential and their partners, who are sexually active, must agree to the use of two highly effective forms of contraception throughout their participation in the study and for three months after last dose of study drug(s), including:

- Condom with spermicide

And one of the following:

- Oral contraceptive or hormonal therapy (e.g. hormone implants)

- Placement of an intra-uterine device

Appendix E provides details of acceptable birth control methods to be used within the study.

## **5.2 Patient enrolment and randomisation**

The Investigator will:

- Obtain signed informed consent from the potential patients before any study-specific procedure is performed.
- Assign potential patient a unique enrolment number, beginning with ‘E0001001’.
- Determine patient eligibility. See Sections 4.1 and 4.2.
- Assign eligible patient a unique patient number, beginning with ‘1001’.

Patients will be randomized into the study provided they have satisfied all patient selection criteria.

If patients have withdrawn their participation in the study after dosing they cannot re-enter into the study.

If a patient withdraws his/her participation in the study, then his/her enrolment/randomization code cannot be reused.

### **5.2.1 Procedures for randomisation**

A randomization list will be produced by using the global randomization system (GRand). Patients will be allocated to one of the three different dose level treatments. The randomization will be done using consecutive randomization codes (patient numbers).

Randomisation codes will be assigned strictly sequentially as patients become eligible for randomisation.

## **5.3 Procedures for handling patients incorrectly enrolled or randomized**

**Patients who fail to meet the inclusion/exclusion criteria** should not, under any circumstances, be randomized or receive study medication. There can be no exceptions to this rule.

Where a patient, who does not meet the selection criteria, is randomized in error and this is identified before dosing, the patient should be withdrawn from the study. A discussion should occur between the AstraZeneca Study Team Physician and the investigator regarding whether a replacement may be considered.

Where a patient, who does not meet the selection criteria, is randomized in error and started on treatment, or where a patient subsequently fails to meet the study criteria post initiation, a discussion should occur between the AstraZeneca Study Team Physician and the investigator regarding whether to continue or discontinue the patient from treatment. If treatment is discontinued the patient should be advised to continue assessments to ensure their safety. In situations where an agreement cannot be reached, the patient should have their study treatment discontinued.

The AstraZeneca Study Team Physician is to ensure all decisions are appropriately documented.

## **5.4 Blinding and procedures for unblinding the study**

This is an open-label study.

## **5.5 Treatments**

### **5.5.1 Identity of investigational product(s)**

**Table 3 Identity of Investigational Product(s)**

Investigational Product	Dosage Form and Strength	Manufacturer
Ticagrelor	Tablet 45 mg	AstraZeneca
Ticagrelor	Tablet 60 mg	AstraZeneca
Ticagrelor	Tablet 90 mg	AstraZeneca

Ticagrelor will be supplied in one bottle containing 14 tablets for each patient.

Ticagrelor tablets will be manufactured and packaged as open-label, patient specific supplies for oral use. The supplies will be labelled in accordance with Good Manufacturing Practice (GMP) and local regulatory requirements.

### **5.5.2 Doses and treatment regimens**

Each patient will receive the following treatments during the treatment visit (Visit 2):

Day 1: ticagrelor (single dose)

Day 3-6: ticagrelor (twice daily/bid)

#### Day 7: ticagrelor (single dose)

On the morning of Day 1, the patients will receive a single 45mg or 60mg or 90 mg dose of ticagrelor (as assigned) under fasting conditions, i.e., patients will fast overnight for at least 8 hours prior to dosing, with water permitted freely except for one hour prior to and following dosing; the patients will take ticagrelor tablets bid on Day 3-6 at least one hour before food. On Day 7, patients will fast overnight for at least 8 hours prior to dosing with water permitted freely except for one hour prior to and following dosing. Patients will receive a single 45 mg or 60 mg dose or 90 mg of ticagrelor in the morning only.

The oral tablet dose will be administered with 240 mL of room temperature water while the patient is sitting in an upright or in a semi-recumbent position. The tablets must not be crushed, chewed, or divided. Meals will be provided on a fixed schedule at the CPU's discretion.

Any patient that vomits within 2 hours after dosing in single dosing days will be considered non-evaluable for PK analysis.

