### 12.1 Description of analysis sets

Throughout the analyses, erroneously treated patients (eg, those randomised to treatment A but actually given treatment B) will be accounted for in the actual treatment group. Patient inclusion in each of the analysis sets will be determined from database lock.

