### **12.1.2 Pharmacodynamic analysis set**

All randomized patients who received at least one dose of investigational product with post-dose PD measurements available and no protocol deviation considered to significantly affect the integrity of PD results (eg, non-compliance with study drug) will be included in the PD analysis set.

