### **12.1.3 Pharmacokinetic analysis set**

All randomized patients who received at least one dose of investigational product with post-dose PK measurements available and no protocol deviation considered to significantly affect PK of ticagrelor and its metabolite, AR-C124910XX, will be included in the PK analysis set.

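### The 2-hour vomiting rule covers PK only and drops the whole patient, so the primary IPA has no stated rule for the same dose

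*Protocol*

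**What the plan says.** Section 5.5.2 of the Protocol, in the text on the Day 1 and Day 7 single doses, states: "Any patient that vomits within 2 hours after dosing in single dosing days will be considered non-evaluable for PK analysis". The rule concerns a patient, not a dosing day, and names PK alone.

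The primary outcome is pharmacodynamic. Section 3.2 says: "The primary variable is IPA, final extent". Table 2 gives PK, IPA and VerifyNow samples one schedule: 0 to 48 h after the Day 1 dose and 0 to 12 h after the Day 7 dose.

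Section 12.1.2 defines the PD set as "All randomized patients who received at least one dose of investigational product with post-dose PD measurements available", with the condition that there be "no protocol deviation considered to significantly affect the integrity of PD results (eg, non-compliance with study drug"). Section 12.1.3 uses the same kind of clause for the PK set, "no protocol deviation considered to significantly affect PK of ticagrelor and its metabolite", and does not repeat the vomiting rule.

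On timing, section 12.1 says: "Patient inclusion in each of the analysis sets will be determined from database lock". Section 5.4 says: "This is an open-label study". Section 10 gives an order of events: clean file is declared, treatment-revealing data may then be added, and the final database is locked.

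**The concern.** The evident reason for the rule is that a dose vomited within 2 hours may not have been absorbed. That reason applies equally to the IPA and PRU measured after the same dose, and to the AUEC and time to peak IPA derived from them. As written, a secondary outcome is protected by a fixed rule, while the primary outcome has only a discretionary clause that may not reach the event.

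Two consequences follow. First, a possibly unabsorbed dose enters the IPA summary of its arm by default, or leaves it through a judgement whose criteria are not set in advance. In arms of 10 to 12 either choice can visibly move the mean. Second, the PK rule removes more than it needs to. Vomiting on Day 7 cannot affect what was measured after the Day 1 dose, yet a literal reading drops that profile too.

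**Working it through.** **Text, set side by side**

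| Question | PK | IPA and PRU |
|---|---|---|
| Named in the 5.5.2 vomiting rule? | Yes | No |
| Sampling times on Days 1 and 7 (Table 2) | 0, 0.5, 1, 2, 3, 6, 12 h; Day 1 continues to 48 h | Identical |
| Exclusion clause in the set definition | Deviation judged to affect PK (12.1.3) | Deviation judged to affect PD integrity (12.1.2) |
| Does the clause clearly cover vomiting? | Not needed, since 5.5.2 applies | No |

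On the last row: intake is supervised and the mouth is checked (section 5.7). That shows the dose was swallowed, not that it was retained. A patient who swallows the dose and then vomits has complied, and the Protocol does not list vomiting as a deviation. The plain reading keeps the patient in the PD set, but the clause leaves room to exclude.

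**Plan figures**

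The synopsis plans 3 × 12 = 36 patients, to give at least 10 evaluable per group. That allows 12 − 10 = 2 non-evaluable patients per group (2/12 = 16.7%). Evaluable for PK, PD or both is not stated. Section 12.3 has no power calculation, and the Protocol gives no expected IPA or SD, so there is no statistical figure to reproduce.

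**Size on Day 1 (assumed gap)**

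Let one patient's IPA at a time point lie *g* points below the mean *m* of the other patients in an arm of *n*. With the patient kept, the arm mean is *m* − *g*/*n*. With the patient excluded, it is *m*. So *g*/*n* is both the bias from keeping the value and the amount by which the decision moves the result. Assume *g* = 20 to 80.

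- n = 12: 20/12 = 1.7 to 80/12 = 6.7 points.
- n = 10: 20/10 = 2.0 to 80/10 = 8.0 points.

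The arm SD, if the others have SD *s*, is √{[(n − 2)s² + ((n − 1)/n)g²]/(n − 1)}. For n = 12 and assumed s = 10:

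- g = 20: √[(1000 + 366.7)/11] = 11.1.
- g = 80: √[(1000 + 5866.7)/11] = 25.0.

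With s = 20 the same formula gives 19.9 and 29.9.

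**Size on Day 7**

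Day 7 follows four days of twice-daily dosing meant to reach steady state (section 3.2). The half-life is given as about 7 h (section 1.1) or about 12 h (section 13). IPA is always calculated against the Day 1 pre-dose value (section 11.3). Drug from Days 3 to 6 is therefore still acting, and a gap near 80 points is not plausible. The shift should be smaller, but the Protocol gives nothing from which to compute it.

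**How often**

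Section 1.3 gives 5-10% for a list of gastrointestinal symptoms that includes vomiting, and no rate for vomiting within 2 h. Applied to the whole list, 36 × 0.05 = 1.8 and 36 × 0.10 = 3.6 patients would be expected to have some such symptom. Early vomiting is only part of that. For assumed per-patient rates *p*, the chance of at least one case is 1 − (1 − *p*)ⁿ:

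| p | arm of 12 | all 36 |
|---|---|---|
| 1% | 11% | 30% |
| 2% | 22% | 52% |
| 5% | 46% | 84% |
| 10% | 72% | 98% |

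**The case against.** A reader might infer that a lost dose is bound to stay in the primary analysis. The text does not say so: section 12.1.2 allows exclusion, and non-compliance is only its example. Retention is the default reading, not a stated rule.

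A reader might also infer that the sets will be chosen with IPA by dose in view. Section 12.1 does not say who decides or what they have seen, open-label treatment does not establish it, and section 10 has a clean-file step before lock. What stands is that nothing shown prevents it.

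Per-day evaluability and sensitivity summaries are often left to the SAP, which is not shown. Their absence alone would be no finding. The point is that section 5.5.2 states a rule, and that rule is too narrow on outcomes and too wide on days. That section 12.1.3 does not repeat it is not an error, since 5.5.2 already governs PK.

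The harm is also limited. The study is descriptive (section 12.3), so no error rate is affected. Medians, ranges, patient listings and individual profiles (section 12.2.3) would reveal an outlying patient. Vomiting within 2 h need not lose the whole dose, and samples drawn before it are unaffected. In a concentration-effect plot (section 11.3.1) a low concentration paired with a low IPA is a legitimate point, so little weight belongs there. Keeping every dosed patient is a defensible PD policy, because exclusion selects on a post-dose event. It would need to be stated, however, and it sits badly beside the opposite policy for PK.

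**Conclusion.** The point holds in a limited form and should be corrected. For the same event on the same day, PK has a fixed rule, while the primary IPA and PRU have only a judgement clause that does not clearly apply. By default the affected IPA stays in. If it is removed, that happens by a decision tied to database lock in an open-label study, with no evidence either way on whether results will have been seen. Separately, the whole-patient wording discards a valid Day 1 PK profile when vomiting occurs on Day 7.

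The size is modest but visible in arms this small: the Day 1 shifts shown above for one affected patient, and less on Day 7. The gap, the SD and the vomiting rates are assumptions. The 80-point end requires near-complete loss of a Day 1 dose and should not be read as the expected effect.

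**What to change.** Reconcile sections 5.5.2, 12.1.2 and 12.1.3 with one rule, applied per dosing day to PK, IPA and PRU:

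- If a patient vomits within 2 h of the Day 1 or Day 7 dose, exclude that day's post-dose PK and PD values from the main summaries.
- List the excluded values and give a sensitivity summary that includes them.
- Keep the other day. The Day 1 pre-dose value also stays, because it is the baseline for Day 7 IPA and PRU. The accumulation ratio needs both days (section 11.2) and is then missing for that patient.

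In section 12.1, settle set membership at the clean-file step of section 10, before PK and PD results are reviewed by dose.

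This changes analysis wording only and leaves dosing and patient care untouched. The cost is a few patient-days lost from the PD summaries, partly offset by Day 1 or Day 7 PK profiles that the present rule would discard. The sensitivity summary shows whether the exclusion matters.
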